#### 266 3.2.1 Pregnancy and breastfeeding

267 There is a high maternal mortality in pregnant women with Ebola Disease, and foetal  
268 survival is rare. There are only three known cases of Marburg Disease in pregnant women.  
269 All women died, and the only neonate delivered died shortly after birth. Therefore, pregnant  
270 women will be eligible for enrolment in the trial. Expert obstetric and teratology advice will  
271 be provided to the Trial Steering Committee prior to the inclusion of a new treatment in the  
272 protocol.

273 WHO recommends breastfeeding should be stopped in a lactating woman with Ebola  
274 Disease. There may be rare circumstances (e.g. a concordantly infected child younger  
275 than six months old without a safe feeding substitute) where a woman with a *Filovirus*  
276 infection continues to breastfeed. These decisions will be made independent of the trial. In  
277 the circumstance that a woman continues breastfeeding she would remain eligible for  
278 enrolment with any dose modifications [specified in virus specific annexes](#).

#### 279 3.2.2 Children

280 Mortality is higher in children compared to adults with Ebola Disease, but the association  
281 between age and death is not certain for Marburg Disease. Children of all ages are eligible  
282 for enrolment. Modifications for children are described [in virus specific annexes](#).

### 283 3.2.3 Vaccination

284 Patients will be eligible for enrolment irrespective of whether they have been vaccinated for  
 285 a filovirus, including the use of experimental vaccines, and vaccines used as post-exposure  
 286 prophylaxis. Vaccination status, including date and name of vaccine, will be recorded for all  
 287 patients.

### 288 3.3 Randomisation

289 Randomisation will be between the following treatment domains in a factorial manner.

290 **Table 1. Randomisation domains.**

Domain	Filovirus x (e.g. SUDV)	Filovirus y ( e.g. EBOV)	Filovirus z (e.g. SUDV)
Randomisation 1 (monoclonal antibody/ies)*	Virus specific monoclonal antibody vs no additional treatment (1:1)	Virus specific monoclonal antibody vs no additional treatment* (1:1)	Virus specific monoclonal antibody vs no additional treatment (1:1)
Randomisation 2 (antiviral)	Antiviral vs no additional treatment (1:1)		
Randomisation 3 (host-directed)	Host directed therapy vs no additional treatment (1:1)		

291 \* Where a licensed monoclonal product exists e.g. MAb114 or REGEN-EB3 for EBOV, patients should receive  
 292 the licensed monoclonal product as part of usual care and would therefore not be randomised into the  
 293 monoclonal domain. However, in some circumstances randomization in this domain may occur (e.g. to test a  
 294 different dose vs. the licensed dose).

296 Randomisation will be done through use of an internet (or, where necessary, telephone)  
 297 based randomisation service. In an effort to prevent the impact of chance imbalances in key  
 298 baseline prognostic factors on the study results, randomisation will, wherever possible, be  
 299 performed with minimisation by such factors. Minimisation factors will be age strata  
 300 (children, younger adults, older adults), viral load, and outbreak. (Where this is not possible,  
 301 simple randomisation will be performed.)

302 If one of the treatments is not available at the site or not suitable for the individual patient  
 303 they will not be eligible for randomisation in that domain but remain eligible for randomisation  
 304 in the other domains. For example, if the monoclonal antibody is not available at the site,  
 305 then a patient may be randomised in the antiviral therapy (antiviral vs. no additional  
 306 treatment) and host-directed therapy (host-directed therapy vs. no additional treatment)  
 307 comparisons only.

### 308 3.4 Interventions

309 Details on the specific treatments included for each virus are described in virus specific  
 310 annexes.

311 **3.5 Study outcomes**

312 **3.5.1 Primary outcome**

- 313
  - All-cause mortality at 28 days following randomisation

314 **3.5.2 Secondary outcome**

- 315
  - Time (days) to *Filovirus* RNA <LLOQ (lower limit of quantitation) within 28 days

316 [Viral clearance, using results from study or routine clinical samples, is defined as

317 the first negative *Filovirus* RT-PCR test without a subsequent positive test result

318 or subsequent death. In the unlikely scenario that a patient is discharged home

319 without two successive negative RT-PCR tests, the date of the first negative test

320 or, if there is no negative test result, the date of medical discharge will be used.]

321 **3.5.3 Other outcomes**

- 322
  - Viral load (measured by cycle threshold) on blood samples taken at Day 3, 5, 7

323 and 10.

324 
  - Progression of organ dysfunction, measured on blood samples taken at Day 3, 5,

325 7, 10.

326 **3.5.4 Safety outcomes**

327 In addition to study outcomes (e.g. mortality), Adverse Events will be recorded if they fall

328 into one of the following groups:

329

- 330 a. Adverse Events of Special Interest (AESIs; e.g. infusion-related reactions).
- 331 b. Serious Adverse Events that are **not considered to be due to the underlying *Filovirus***
- 332 **infection.**
- 333 c. Serious (per standard regulatory definition) that are considered with reasonable
- 334 probability to be related to one of the study medications (i.e. Suspected Serious
- 335 Adverse Reactions, which includes Suspected Unexpected Serious Reactions
- 336 [SUSARs]).
- 337

338 Pregnancy and foetal outcomes will also be recorded.

339

340 Study outcomes will be assessed based on data recorded up to the time of death, hospital

341 discharge or 28 days after randomisation (whichever occurs first). Pregnant women will be

342 followed up to completion of pregnancy.

343

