### 351 4.1 Main analysis approach

352 For all each randomised comparison, the outcomes will be made between all participants  
353 randomised to the different treatment comparisons, irrespective of whether they received  
354 some, none, or all of their allocated treatment (i.e. these comparisons will be based on  
355 “intention-to-treat” analyses).

356 The primary analyses will involve pairwise comparisons between the active ‘experimental’  
357 and ‘reference’ arms as follows:

- 358 • Effect of monoclonal antibody: monoclonal vs. no additional treatment.
- 359 • Effect of antiviral: antiviral vs. no additional treatment.
- 360 • Effect of host-directed therapy: host-directed therapy vs no additional treatment.

361 Logistic regression adjusted for baseline levels of key prognostic factors will be used to  
362 estimate the conditional odds of 28-day mortality for each treatment group relative to its  
363 control (ie, the 28-day conditional odds ratio) and its 95% confidence interval. A two-tailed  
364 P-value <0.05 will be considered as statistically significant. Logistic regression (based on  
365 vital status at Day 28, regardless of the time to death within this 28-day range) will be used  
366 in preference to Cox regression because the latter might give undue weight to the exact  
367 times of death of the very poor-prognosis patients (thereby giving inadequate weight to the  
368 death or survival of the better-prognosis patients). However, for illustrative purposes,  
369 Kaplan-Meier plots showing the pattern of survival over the first 28 days will also be created,  
370 both overall and within prognostic categories. For the primary objective of assessing the  
371 effects of each study treatment on 28-day mortality, discharge alive before day 28 will be  
372 assumed as survival to day 28 (unless there are additional data confirming otherwise).

373 For the secondary objective of assessing the effects of each treatment on time to filovirus  
374 RNA <LLOQ within 28 days, differences in median days to filovirus RNA <LLOQ will be  
375 tested using the Wilcoxon rank-sum test, imputing deaths prior to day 28 as the worst ranks,  
376 with earlier deaths having a worse rank than later deaths. The study will collect viremia data  
377 at baseline and approximately days 3, 5, 7, 10. Patients who are discharged from inpatient  
378 care but without an available *Filovirus* RT-PCR test result will be assumed to have *Filovirus*  

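### Section 3.5.2: the fallback date for viral clearance omits the condition of no later positive, so a negative that a later test contradicted can be scored as clearance

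*Protocol*

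**What the plan says.** The protocol has one secondary outcome, in section 3.5.2: time in days to filovirus "RNA <LLOQ (lower limit of quantitation) within 28 days". The bracketed text beneath it contains two rules.

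- **Main definition.** Clearance is "the first negative *Filovirus* RT-PCR test without a subsequent positive test result", or subsequent death. It does not require a second, confirming negative.
- **Fallback.** This begins "In the unlikely scenario that a patient is discharged home" and applies to patients who leave "without two successive negative RT-PCR tests, the date of the first negative test". The sentence ends "or, if there is no negative test result, the date of medical discharge will be used". The discharge date is therefore used only when the patient has no negative result at all.

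Section 4.1 compares the resulting times with a Wilcoxon rank-sum test in which deaths before day 28 take the worst ranks. It says that viraemia is collected "at baseline and approximately days 3, 5, 7, 10". The schedule in section 6.7 adds a study RT-PCR at death or discharge and records clinically obtained results on other days. Section 4.1 also assumes clearance on the day of discharge for patients with no available RT-PCR result, with an exception where the evidence in a particular case says otherwise.

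**The concern.** The main definition already handles a single unconfirmed negative: if no positive follows, that negative is the clearance date. For patients discharged alive with at least one negative, the fallback can therefore change the date only if a positive followed the first negative. That is exactly the case the main definition was written to exclude. As worded, the fallback is either redundant or it overrides the main rule.

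A patient known to be positive after the negative test would then receive an early, favourable rank in the rank-sum test. The error can run in one direction only, towards earlier clearance.

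**Working it through.** No stated figure needs reproducing, because the point concerns a definition. The check applies both rules to test sequences. P is a positive and N a negative RT-PCR; all patients are discharged alive.

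**Rules as applied**

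- Main: the day of the first N with no later P; otherwise no clearance.
- Literal fallback, used when the sequence contains no NN: the day of the first N; if there is no N, the day of discharge.

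**Records that include the discharge test scheduled in section 6.7**

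| Record | Main | Literal fallback | Difference |
|---|---|---|---|
| P day 3, N day 5, P day 7, N at discharge day 8 | day 8 | day 5 | 8 − 5 = 3 days too early |
| P day 3, N day 5, P day 7, P at discharge day 8 | none | day 5 | a date where none was shown |
| P day 3, P day 5, N day 7, discharged day 8, no further test | day 7 | day 7 | none |

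In the second record the discharge-date branch is closed, because a negative exists.

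**All patterns on days 3, 5, 7 and 10** (assuming all four samples taken, discharge on day 11 and no other test)

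There are 2 × 2 × 2 × 2 = 16 patterns. Eight contain two successive negatives and stay under the main definition. The other eight fall under the fallback:

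| Pattern | Main | Literal fallback |
|---|---|---|
| PPPP | none | day 11 (discharge) |
| PPPN | day 10 | day 10 |
| PPNP | none | day 7 |
| PNPP | none | day 5 |
| PNPN | day 10 | day 5 |
| NPPP | none | day 3 |
| NPPN | day 10 | day 3 |
| NPNP | none | day 3 |

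In six of these eight (all except PPPP and PPPN) the literal fallback dates clearance from a contradicted negative. Two are dated too early: PNPN by 10 − 5 = 5 days and NPPN by 10 − 3 = 7 days. Four receive a date although the main definition gives none. If the patient leaves after the day 7 test, NPN adds an error of 7 − 3 = 4 days. On this grid a dating error needs negative, positive, negative with no NN, so 4, 5 and 7 days are the only possible values. Discharge or clinical tests on other days give other gaps, such as the 3 days above.

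**Internal consistency**

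PNNP has two successive negatives, so the main definition applies and the patient is not cleared. PNPP has one negative, so the fallback applies and the patient is cleared on day 5. The patient with more negative results is scored worse.

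These are counts of possible patterns, not expected frequencies.

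**The case against.** **The fallback may refer back to the main definition.** It follows directly on that definition, so its first negative test can be read as the first negative with no later positive. This is a fair reading and may be what was meant. But the branch then only repeats the main rule, and a patient who is negative, then positive, then discharged is covered by neither branch: no negative qualifies, yet a negative exists, so the discharge date is not available. The text needs correcting on either reading.

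**The exception in section 4.1 might cover it.** It does not. It is attached to patients with no available RT-PCR result, and these patients have results.

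**The discharge test often removes the case.** This stands in part. A patient who is PNPN to day 10 and negative again at discharge has two successive negatives and returns to the main definition, so the pattern table is incomplete for anyone with a discharge result. The first two worked records include a discharge test and the problem remains. Section 8.4 also allows research samples to be missed.

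**The situation is rare and the outcome is not primary.** This stands. The protocol calls the situation unlikely and gives no frequency.

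**A stronger inference to avoid.** A reader might infer that the rule favours an arm with earlier discharge, since treatment is open-label and early discharge leaves fewer chances of two successive negatives. The document does not support that. A contradicted negative needs time for a negative and then a positive. Counting patterns without NN, the contradicted ones are 1 of 3 after two tests (NP), 3 of 5 after three (PNP, NPP, NPN) and 6 of 8 after four. Such counts are not frequencies, but they give no support to the idea that earlier discharge produces more of these errors.

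**Conclusion.** The point holds as a minor error in an endpoint definition. Taken literally, section 3.5.2 counts as clearance a negative that the trial's own later test contradicts, and it orders patients inconsistently. For an affected patient the date is 4, 5 or 7 days too early on the planned sampling days, or a date is given where none was shown.

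The effect on the treatment comparison cannot be sized from the protocol, because that depends on how many patients go home without two successive negatives and how often results alternate, and neither is given. Since the protocol expects the situation to be unlikely, the overall effect is probably small. The primary outcome is untouched. No difference between arms is demonstrated, and nothing here bears on when patients should be discharged.

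The conclusion rests on the literal wording. On the back-reference reading the misdating disappears, but the gap for a patient who is negative, then positive, then discharged remains.

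**What to change.** Reword the fallback in section 3.5.2 so that, for a patient discharged without two successive negatives, the date used is *the date of the first negative test that is not followed by a positive test*. On the grid above, PNPN and NPPN then move to day 10, PPPN stays at day 10, and PPNP, PNPP, NPPP and NPNP have no qualifying negative.

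The second step is therefore needed as well: state one scoring rule for every patient discharged alive whose results include no qualifying negative. It should treat alike a patient with a contradicted negative (PNPP), one with two negatives and then a positive (PNNP), and one positive at every test (PPPP). Ranking only the first group as not cleared, while PPPP keeps its discharge date as clearance, would replace one inconsistency with another. Either a common discharge-date rule or a common not-cleared rank ahead of deaths would be consistent; the choice should be made before unblinding. The section 4.1 assumption for patients with no RT-PCR result can stay as a separate case.

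The cost is one or two sentences in section 3.5.2 and the matching derivation in the statistical analysis plan. Test dates and results are already recorded, so no new data are needed. If the common rule changes how PPPP is scored, the existing no-negative branch must be amended openly.

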## 344 4 STATISTICAL ANALYSIS

345 All analyses for reports, presentations and publications will be prepared by the Statistical  
346 Analysis Team. [The purpose of this section is to describe the main statistical approaches to  
347 be used in the trial.](#) Additional technical details (e.g. cut points for subgroup analyses) will  
348 be defined by the Trial Steering Committee and Statistical Analysis Team prior to any  
349 unblinding of effects of study treatments and made publicly available (including any  
350 subsequent revisions) .

### 351 4.1 Main analysis approach

352 For all each randomised comparison, the outcomes will be made between all participants  
353 randomised to the different treatment comparisons, irrespective of whether they received  
354 some, none, or all of their allocated treatment (i.e. these comparisons will be based on  
355 “intention-to-treat” analyses).

356 The primary analyses will involve pairwise comparisons between the active ‘experimental’  
357 and ‘reference’ arms as follows:

- 358 • Effect of monoclonal antibody: monoclonal vs. no additional treatment.
- 359 • Effect of antiviral: antiviral vs. no additional treatment.
- 360 • Effect of host-directed therapy: host-directed therapy vs no additional treatment.

361 Logistic regression adjusted for baseline levels of key prognostic factors will be used to  
362 estimate the conditional odds of 28-day mortality for each treatment group relative to its  
363 control (ie, the 28-day conditional odds ratio) and its 95% confidence interval. A two-tailed  
364 P-value <0.05 will be considered as statistically significant. Logistic regression (based on  
365 vital status at Day 28, regardless of the time to death within this 28-day range) will be used  
366 in preference to Cox regression because the latter might give undue weight to the exact  
367 times of death of the very poor-prognosis patients (thereby giving inadequate weight to the  
368 death or survival of the better-prognosis patients). However, for illustrative purposes,  
369 Kaplan-Meier plots showing the pattern of survival over the first 28 days will also be created,  
370 both overall and within prognostic categories. For the primary objective of assessing the  
371 effects of each study treatment on 28-day mortality, discharge alive before day 28 will be  
372 assumed as survival to day 28 (unless there are additional data confirming otherwise).

373 For the secondary objective of assessing the effects of each treatment on time to filovirus  
374 RNA <LLOQ within 28 days, differences in median days to filovirus RNA <LLOQ will be  
375 tested using the Wilcoxon rank-sum test, imputing deaths prior to day 28 as the worst ranks,  
376 with earlier deaths having a worse rank than later deaths. The study will collect viremia data  
377 at baseline and approximately days 3, 5, 7, 10. Patients who are discharged from inpatient  
378 care but without an available *Filovirus* RT-PCR test result will be assumed to have *Filovirus*  
379 RNA <LLOQ on their day of discharge (unless in a particular case there is good evidence to  
380 the contrary).

381 For each treatment, the main comparisons will ignore any other treatments that the patient  
382 may have been randomised to in a factorial manner. However, subgroup analyses of each  
383 treatment effect will include analyses by such factorial treatments.

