60 included are determined by expert consultations convened by WHO. If clear evidence of  
61 efficacy, futility, or a safety signal are not achieved for any of the comparisons during a given  
62 outbreak, the protocol permits the continuation of relevant arms of the trial in future filovirus  
63 outbreaks until a clear result is achieved.

64

[figure not shown]
65 **Protocol structure** (see figure 1 below): The trial design permits continued operations even  
66 when:

- 67 i. Promising new treatments are developed and are ready to be tested;
- 68 ii. Treatments no longer require evaluation in a trial because they have been shown to  
69 be effective or ineffective or unsafe;
- 70 iii. New countries wish to join the trial with their own regulatory requirements;
- 71 iv. Outbreaks of different filoviruses occur with different treatment options;
- 72 v. New filoviruses emerge.

73 This core protocol details the key requirements of the trial irrespective of the location or  
74 cause of an outbreak but is supplemented by appendices that describe more detailed  
75 information for an outbreak in a particular regulatory jurisdiction (Country appendices), or  
76 for a particular virus (Virus appendices). The country appendices name national  
77 investigators and partner institutions. They specifically detail adaptations to comply with  
78 local regulatory requirements. These are usually governance requirements, ethics  
79 considerations (such as proxy or minor consent processes) and changes to reporting  
80 timelines. The virus appendices provide details of the treatments to be evaluated for a  
81 particular filovirus, and any data collection additions.

82 The protocol sits alongside a detailed statistical analysis plan that will provide a pre-specified  
83 plan for assessing treatment safety and efficacy. Standard operating procedures provide  
84 site-level detail on how to interpret and implement the protocol.

85

86 **Figure 1: Protocol structure**

87

88

89 **Eligibility and randomisation:** This is a randomised controlled trial for patients receiving  
 90 inpatient care for laboratory-confirmed acute filovirus disease. In a factorial design, eligible  
 91 patients are randomly allocated (1:1) in one or more comparisons.

92

- 93 ● Monoclonal antibodies:
  - 94 ○ Targeted monoclonal antibody/cocktail\* vs no additional treatment
- 95 ● Virus-directed therapy:
  - 96 ○ Antiviral therapy\* vs no additional treatment

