#### 391 4.1.2 Adjustment for baseline characteristics

392 The main logistic regression analyses described above will adjust for important prognostic  
393 markers recorded at baseline (eg, age, RT-PCR Ct value, virus type, and time since  
394 symptom onset). This provides a safeguard against the impact that any chance imbalances  
395 in their frequencies between randomised groups may have on the randomised comparisons.  
396 In addition, even if there were no such imbalances, adjustment for baseline characteristics  
397 somewhat increases statistical power by ensuring that, effectively, better-prognosis patients  
398 are compared only with each other and that worse-prognosis patients are compared only  
399 with each other. [Exact details of the prognostic factors adjusted for in the logistic regression  
400 analyses will be provided in the SAP prior to any unblinded analyses being done.](#)

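### The viral-clearance outcome is tested by an unadjusted Wilcoxon test despite minimisation on viral load: conservative where viral load is strongly prognostic, and inefficient

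*Protocol*

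**What the plan says.** Section 4.1 names the test for time to filovirus RNA below the limit of quantitation: differences are "tested using the Wilcoxon rank-sum test, imputing deaths prior to day 28 as the worst ranks", "with earlier deaths having a worse rank than later deaths". It gives no stratification and no covariates.

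For mortality, the same section says "Logistic regression adjusted for baseline levels of key prognostic factors will be used to" estimate the odds ratio. Section 4.1.2 covers adjustment and is confined to that model: "The main logistic regression analyses described above will adjust for important prognostic" markers, with age, Ct value, virus type and time since onset as examples. It adds that adjustment "somewhat increases statistical power by ensuring that, effectively, better-prognosis patients" are compared only with one another.

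Allocation is 1:1 (Synopsis). Section 3.3 minimises, wherever possible, on age strata ("children, younger adults, older adults), viral load, and outbreak". Otherwise "simple randomisation will be performed".

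Section 4.2 gives a 120-patient example in two prognostic halves that follow Ct value. Mortality falls from 30% to 10% in one half and from 90% to 70% in the other, and the result is obtained by combining the two strata.

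**The concern.** Deaths take the worst ranks, so the secondary outcome inherits the mortality gradient across viral load. If allocation balances a strong predictor and the analysis ignores it, the standard error is calculated as if chance imbalance in that predictor could still occur. The standard error is then too large, the P-value tends to be too large, and power falls.

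The protocol's own argument in 4.1.2 for comparing like with like applies equally here, and the baseline variables are already collected for the primary model. Section 4.2 accepts that a single outbreak may yield small numbers, which is where lost efficiency matters most.

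**Working it through.** **Protocol figures first.** The 120-patient example has 30 per arm in each half, with expected deaths of 3 v 9 and 21 v 27.
- Stratified (Mantel-Haenszel): observed minus expected is −3 − 3 = −6. Each stratum has variance 30×30×12×48/(60²×59) = 2.441. So z = −6/√4.881 = −2.72 and 2P = 0.0066, which agrees with the stated 2P<0.01.
- Unstratified, 24/60 v 36/60: z = −2.18 and 2P = 0.029.

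The protocol's claim for mortality therefore depends on stratifying. The 520-patient calculation also reproduces: 258 per arm are needed for 50% v 33.3% at 90% power and 2P=0.01. The protocol states no size or power for the Wilcoxon test.

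**Size by formula.** Scale the ranks to 0–1, with variance 1/12. Deaths and survivors form two blocks whose mean ranks differ by 0.5. If clearance and death times do not depend on viral load, 30% v 90% mortality separates the halves by 0.6×0.5 = 0.30. The share of rank variance explained is R² = (0.30/2)²/(1/12) = 0.27. With viral load balanced, the true size of the nominal 5% test is 2×[1−Φ(1.96/√(1−R²))] = 2×[1−Φ(2.294)] = 2.2%. For 30%/70%, R² = 0.12 and the size is 3.7%. For 40%/60%, R² = 0.03 and the size is 4.7%.

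**Size by simulation.** Minimisation on viral load (2 levels), age (3) and outbreak (2), with biased-coin probability 0.8 or 1.0. The two viral-load levels, the number of outbreaks, the coin and the time distributions are assumptions.

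| Mortality in the two halves | N | Times independent of viral load | Times dependent on viral load |
|---|---|---|---|
| 30% / 90% | 120 | 2.1–2.7% | 1.4% |
| 30% / 90% | 520 | 2.1% | 1.2% |
| 30% / 70% | 120 | 3.6–3.8% | 2.1–2.3% |
| 30% / 70% | 520 | 3.7% | 2.2% |
| 40% / 60% | 120 | 4.3–4.5% | 3.0–3.2% |
| 40% / 60% | 520 | 4.7% | 3.9% |

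A repeat simulation gave about 1.3–3% at 30%/90% and about 4–6% at 40%/60%. Tests stratified by viral load stayed at 4.1–5.9% throughout. Under simple randomisation at 30%/90%, the unadjusted test had size 5.2% (N=120) and 5.1% (N=520).

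**Power by formula, 120-patient example, two-sided 5%.** Assume no effect on clearance time and times independent of viral load. Average mortality is 60% v 40%, so mean ranks differ by 0.20×0.5 = 0.10. The standard error is √[(1/12)(1/60+1/60)] = 0.0527, giving z = 1.897.
- Unadjusted: true SD of z is √0.73 = 0.854, so power is Φ((1.897−1.96)/0.854) = 47%.
- Stratified by viral load on overall ranks: z = 1.897/0.854 = 2.22, so power is Φ(2.22−1.96) = 60%.
- Van Elteren by viral load: re-ranking within strata restores the within-stratum variance to 1/12. The difference is again 0.10, so z = 1.897 with SD 1 and power is Φ(−0.063) = 47%. The size is corrected but almost no power is gained.

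**Power by simulation, same example.**

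| Times | Unadjusted | Van Elteren | Stratified, overall ranks |
|---|---|---|---|
| Independent of viral load | 48% | 49% | 62% |
| Dependent on viral load | 35% | 49% | 58% |

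At 40%/60% mortality, in scenarios that also shorten clearance, the gain was 0–2 points, or about 7 if times depend on viral load.

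**Splitting by outbreak.** In the 120-patient example with times independent of viral load, van Elteren by viral load and outbreak gave 43.5% v 47.2% for the plain Wilcoxon with 4 outbreaks, and 40.2% v 46.0% with 8. The numbers of outbreaks are assumed.

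**The case against.** A plain rank test is simple and valid, and here it errs on the safe side. The outcome is secondary, and mortality, which supplies the worst ranks, is already tested with adjustment. All of this stands and limits the point to efficiency.

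Section 4 also presents itself as the main approaches, with technical detail to follow, so the SAP (not available for this review) might add strata. That is possible. But 4.1.2 defers only the choice of covariates for the logistic model. The protocol itself names the rank test, and as named it is unadjusted.

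A reader might infer that the true error is about 2% in general. The documents do not support that. The figure belongs to the 30%/90% illustration with minimisation in force, and Section 3.3 allows simple randomisation, under which size is nominal. A reader might also infer that clearance depends on viral load as strongly as mortality does. The protocol links viral load to severity and death only. The power figures for the dependent case rest on that assumption, so both cases are shown.

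**Conclusion.** The point holds as an efficiency loss on a secondary outcome. It is not a validity problem, and there is no false-positive inflation. With minimisation and the protocol's own 30%/90% gradient, true size is about 1.2% to 3%. It is about 3% to 6% at 40%/60%, and about 5% under simple randomisation.

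In the 120-patient example, power is about 35–48% unadjusted and about 58–62% with a viral-load-stratified test on overall ranks. Van Elteren by viral load gives about 47–49%, a gain of 0 to 14 points. These power figures depend on assumed clearance and death times. It would go too far to conclude that real antiviral effects will be missed, or that any stratified test helps at no cost.

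**What to change.** In Section 4.1, keep the ranking as it is and state that its analysis is adjusted for the primary-analysis covariates, including baseline Ct. Two forms would serve:
- a proportional-odds model on the ranked outcome with those covariates; or
- a rank-sum test on overall ranks stratified by baseline viral-load group. Sum over groups the treated rank sum minus its within-group expectation, m×(mean rank), and divide by the square root of the summed within-group variances, m(n−m)/n × s². Here n is the group size, m the number treated and s² the variance of the overall ranks in the group.

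Do not use a van Elteren test cross-classified by viral load and outbreak, since sparse strata can cost power. Choose the form before unblinding. The cost is a sentence in 4.1 and slightly more analysis work, with no new data. The proportional-odds option adds a modelling assumption.
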